4.6.2. Sensitivity analyses

To assess the robustness of findings from the primary analysis, the following set of sensitivity analyses will be performed:

• Analyses that involve imputing missing values for saliva screens or self-report surveys will be repeated without imputing missing values. That is, they will be left as missing, and proportions will use the total number non-missing values available as the denominator. The primary analysis will be repeated for the PP population as defined in Section 3 if less than 90% of the ITT population is in the PP population.

4.7. Secondary Estimand Analyses

The secondary efficacy objectives are:

- 1. To evaluate the efficacy of IXT-m200 in improving participant-rated quality of life.
- 2. To evaluate the efficacy of IXT-m200 in increasing the number of participants achieving early remission.
- 3. To evaluate the efficacy of IXT-m200 in improving clinician-rated response to treatment.
- 4. To evaluate the efficacy of IXT-m200 in improving patient-rated response to treatment.

4.7.1.1. Definition of endpoints

The corresponding secondary endpoints are:

- 1. Change from screening in participant-rated quality of life as measured by the Treatment Effectiveness Assessment (TEA) at Week 13, 25, and Week 33.
- 2. Responders at Week 25 as measured by the DSM-5 criteria. A responder is a participant who meets the definition of early remission, i.e., ≥3 months and <12 months without meeting DSM-5 criteria, while disregarding the result for craving.
- 3. Difference between groups in Clinical Global Impression of Change (CGIC) at Week 13, 25, and Week 33.
- 4. Difference between groups in Patient Global Impression of Change (PGIC) at Week 13, 25, and Week 33.

4.7.1.2. Main analytical approaches

All secondary analyses will use the ITT population.

Quality of life analysis

A secondary objective is to evaluate the efficacy of IXT-m200 in improving patient-rated quality of life, as measured by change from screening in the Treatment Effectiveness Assessment score at Week 13, Week 25, and Week 33.

The Treatment Effectiveness Assessment includes four items with 10 ordinal response options ranging from "not well at all" to "extremely well" (Likert scale), where higher values indicate better quality of life. The Treatment Effectiveness Assessment score is the sum of the four responses (minimum = 4, maximum = 40); the Treatment Effectiveness Assessment score will not be computed if the participant did not respond to all four items.

As the sum of four ordinal items, a nonparametric approach to the analysis will be used since it is unlikely the values will meet the necessary normality assumptions for MMRM or ANCOVA

methods. Therefore, the change from screening in Treatment Effectiveness Assessment score at each post-screening timepoint will be compared in each IXT-m200 group versus the placebo group using a Kruskal-Wallis test.

For each comparison and timepoint, the Hodges-Lehmann estimate and 95% confidence intervals for the difference in group medians, and two-sided p-values will be reported.

A waterfall plot, depicting the median change from baseline at each timepoint will be provided for each treatment group. Pseudo-R code for the plot is included in Exhibit 4. Exhibit 5 contains an example of the waterfall plot.

[figure not shown]
Exhibit 4 Pseudo-R Code for TEA Waterfall Plot

```
coltrt <- ifelse(medstrt >= 0,rgb(0.2,0.7,0.9,.75), rgb(1,0.5,0,.75))
colplcbo <- ifelse(medsplcbo >= 0,rgb(0.2,0.7,0.9,.75), rgb(1,0.5,0,.75))

par(mfrow=c(1,2))
barplot(medstrt,ylim=c(min(c(medstrt,medsplcbo)),max(c(medstrt,medsplcbo))),col=coltrt,yla
b="Change from Baseline")
segments(x0=0,x1=4,y0=0,y1=0,lty="dashed")

title('Change from Baseline in TEA Score for IXT-m200 Group')
axis(1, at=1:3, labels=c("Week 13","Week 25", "Week 33"))
barplot(medsplcbo,ylim=c(min(c(medstrt,medsplcbo)),max(c(medstrt,medsplcbo))),col=colplc bo)
title('Change from Baseline in TEA Score for Placebo Group')
axis(1, at=1:3, labels=c("Week 13","Week 25", "Week 33"))
segments(x0=0,x1=4,y0=0,y1=0,lty="dashed")
```

Exhibit 5 TEA Waterfall Plot

Proportion of responders meeting early remission criteria

A secondary objective is the proportion of responders at Week 25 as measured by DSM-5 criteria. A responder is a participant who meets the definition of early remission, i.e., ≥3 months and <12 months without meeting DSM-5 criteria, while disregarding the result for craving. All other criteria, 10 in total, will be counted. Participants that withdraw or discontinue prior to Week 5, or do not have any reported saliva or self-report use data between Weeks 5 and 25 will not be included in the analysis.

The proportion of participants achieving a response will be compared in each IXT-m200 dose group versus the placebo group using a stratified Mantel-Haenszel statistic with stratification level of past-month METH use at screening (discrete). The output will provide the risk difference between each IXT-m200 dose group and the placebo group, two-sided p-values, and 95% confidence intervals using the Miettinen-Nurminen (score) confidence limits⁴.

Clinician-rated response to treatment

A secondary objective is to evaluate the efficacy of IXT-m200 in improving clinician-rated response to treatment, as measured by Clinical Global Impression of Change (CGIC) at Week 13, 25, and Week 33. The CGIC is completed by the clinician and has seven ordinal responses (Likert scale) ranging from "very much improved" to "very much worse". The comparison between groups will be conducted using a nonparametric Kruskal-Wallis test. The percentage of subjects in each scale category will be tabulated by treatment group and timepoint, and a graphical display using a frequency polygon will be produced for the Week 25 values.

Patient-rated response to treatment

Another secondary objective is to evaluate the efficacy of IXT-m200 in improving patient-rated response to treatment as measured by the Patient Global Impression of Change (PGIC) at Week 13, 25, and Week 33. PGIC is completed by the patient and has seven ordinal responses (Likert scale) ranging from "very much improved" to "very much worse".

The comparison between groups will be conducted using a nonparametric Kruskal-Wallis test. The percentage of subjects in each scale category will be tabulated by treatment group and timepoint, and a graphical display using a frequency polygon will be produced for the Week 25 values.

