9.4.3.3 TREATMENT EFFECTIVENESS ASSESSMENT

The third secondary efficacy endpoint is the difference between groups in the change from screening in participant-rated quality of life as measured by the Treatment Effectiveness Assessment (TEA) at Weeks 13, 25, and 33.

The Treatment Effectiveness Assessment includes four items with 10 ordinal response options ranging from “not well at all” to “extremely well” (Likert scale), where higher values indicate better quality of

life⁵. The Treatment Effectiveness Assessment score is the sum of the four responses (minimum = 4, maximum = 40); the Treatment Effectiveness Assessment score will not be computed if the participant did not respond to all four items.

Change from screening in Treatment Effectiveness Assessment scores at each post-screening timepoint will be compared in each IXT-m200 group versus the placebo group using a mixed model for repeated measures (MMRM), which assumes unobserved values are missing at random. The dependent variable is change from screening in Treatment Effectiveness Assessment score. The independent variables in each model will include treatment group, stratification level of past-month METH use at screening, screening Treatment Effectiveness Assessment score; visit, and treatment group by visit interaction term. In the event that the model does not converge, then an ANCOVA model will be fit with the change from baseline at the final timepoint as the outcome, baseline outcome value, treatment group, and stratification factor as covariates in the model. For each comparison and timepoint, the adjusted means and standard errors for each treatment group and the estimated difference between the groups and associated 95% confidence intervals and two-sided p-values will be reported.

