PROTOCOL TITLE	OUTLAST: A Phase 2 Double-Blind, Randomized, Placebo- Controlled, Multiple-Dose Study to Evaluate the Safety and Efficacy of IXT-m200 in Treatment-Seeking Individuals with Methamphetamine Use Disorder	
SAP Version, Date	V5, 01May2024	
SAP AUTHOR	[name] Director, Biostatistics EMB Statistical Solutions, LLC	
Investigational Product	IXT-m200	
Protocol Number	M200C-2201	
Protocol Version, Date	5 03Feb2023	
Signature Statement By my signature, I indicate I have reviewed this SAP and find its contents to be acceptable.		
Reviewers on behalf of InterveXion Therapeutics, LLC		
Approver Signature	Date	
_	[name], MBA, PhD Chief Operating Officer Sponsor	

1. Introduction

The purpose of this SAP is to describe the analysis variables and statistical procedures that will be used to analyze and report the results of InterveXion's protocol M200C-2201. This study is a Phase 2A study evaluating the safety, efficacy, immunogenicity, and pharmacokinetics (PK) of IXT-m200, a chimeric anti-methamphetamine monoclonal antibody treatment, in treatment-seeking individuals with methamphetamine (METH) use disorder (MUD). This statistical analysis plan (SAP) is based on InterveXion's protocol M200C-2201 version 5, dated February 3, 2023.

The SAP was written in accordance with the recommendations outlined in the International Conference on Harmonization (ICH) E9 Guideline entitled "Guidance for Industry: Statistical Principles for Clinical Trials" and the ICH-E3 Guideline entitled "Guidance for Industry: Structure and Content of Clinical Study Reports".

Some of the analyses detailed here may be more explicit or in some respects different from those stated in the protocol. In case of differences, this SAP supersedes the statistical sections in the protocol.

Most statistical analyses will be performed using SAS® version 9.4 or later, with SAS program code prepared specifically for the project by qualified statisticians and SAS programmers. Other validated programs (e.g., S-Plus, R) may be used for graphs or for specialized analyses.

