1.1. Objectives, Endpoints, and Estimands

The following Table 2 lists the primary and secondary efficacy objectives of the study, along with the endpoints that will be measured, the clinical question to be addressed, as well as the estimand. An estimand is defined in the ICH E9(R1) guidance as "...the target of estimation to address the scientific question of interest posed by the trial objective."

Table 2 Primary and Secondary Efficacy Objectives, Endpoints and Estimands

Primary		
Objective: To evaluate the efficacy of IXT-m200 in preventing or	Endpoints: Percent of 20 weeks abstinent from stimulants following a 4-week grace period (between Week 5 and Week 25) as measured by saliva screens.	
reducing relapse to stimulant use.	Clinical Question: Does adding IXT-m200 to standardized cognitive behavioral therapy (CBT) program improve the percent of 20 weeks abstinent from stimulants following a 4-week grace period, relative to the CBT program alone, in treatment-seeking participants, regardless of IXT-m200 interruption or discontinuation, for any reason?	
	Estimand: The difference in group means between the IXT-m200 and placebo groups for the percent of 20 weeks abstinent from stimulants following a 4-week grace period as measured by saliva screens in treatment-seeking individuals with MUD. All observations will be used, regardless of whether a participant discontinued treatment early. All missing values will be imputed assuming the participant is not abstinent.	
	Secondary	
Objective: To evaluate the efficacy of IXT-m200 in improving	Endpoints: Change from screening in participant-rated quality of life as measured by the Treatment Effectiveness Assessment (TEA) at Week 13, 25, and Week 33.	
participant-rated quality of life.	Clinical Question: Does adding IXT-m200 to standardized CBT program improve the change from screening in participant-rated quality of life relative to the CBT program alone in treatment-seeking participants regardless of IXT-m200 interruption or discontinuation, for any reason?	
	Estimand: The difference in group medians for the change from screening in participant-rated quality of life at Week 13, 25, and 33 between the IXT-m200 and placebo groups. All observations will be used, regardless of whether a participant discontinued treatment early. Missing values will not be imputed.	

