1.2. Study Design

InterveXion's protocol M200C-2201 is a Phase 2, double-blind, placebo-controlled, multiple-dose study of the safety and efficacy of monthly intravenous (IV) doses of IXT-m200 in treatment-seeking individuals with METH use disorder. The study was stopped before enrolling Cohort 2. As such, any reference to Cohort 2 in this document no longer applies, but has been retained for reference.

The study consists of two cohorts:

- In Cohort 1, approximately 60 participants will be randomized in a 2:1 ratio to IXT-m200 1.5 g or placebo (saline).
- In Cohort 2, approximately 60 participants will be randomized in a 2:1 ratio to the recommended dose of IXT-m200 or placebo based on the interim analysis at the end of Cohort 1. If the interim analysis recommends maintaining a dose of 1.5 g, then the sample size will be recalculated.

In each cohort, participants will receive either study drug (IXT-m200 at the cohort-specific dose or placebo) at the beginning of Weeks 1, 5, 9, 13, 17, and 21. All participants will also participate in seven sessions of a standardized cognitive behavioral therapy (CBT) program which will be delivered by a trained therapist; the first dose of IXT-m200 or placebo is intended to be given on the same day of initiation of CBT. For Cohort 1, the participants will participate in the CBT sessions during their monthly visits. For Cohort 2, participants will go to the clinic weekly for saliva drug tests and will participate in CBT sessions every two weeks, starting with Week 1. Participants will be followed at monthly intervals through Week 33. Cohort 1 will use app-based assessments to monitor between visits and Cohort 2 will use TLFB to monitor between visits. Schema 1.2 in the protocol displays the schematic of the study design for Cohort 1, and Appendix 1 shows the schedule of events. The first four weeks of treatment will be considered a grace period, designed to accommodate the likelihood that participants will relapse initially and experience the effects of IXT-m200. It further allows participants time to absorb and incorporate some of the skills taught by cognitive behavior therapy. METH use endpoints will be analyzed in the weeks following the grace period.

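### The SAP's Kruskal-Wallis test of TEA change drops the protocol's screening-score and METH-use adjustment; non-normality does not require that, and precision is usually lost

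*SAP*

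**What the plan says.** Protocol section 9.4.3.3 compares TEA change between groups with a "mixed model for repeated measures (MMRM), which assumes unobserved values are missing at random". On covariates it states: "The independent variables in each model will include treatment group, stratification level of past-month METH use at screening, screening Treatment Effectiveness Assessment score", followed by visit and the treatment-by-visit interaction. If that model does not converge, the fallback is an ANCOVA that still contains the baseline score and the stratification factor.

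The SAP's Introduction says that "this SAP supersedes the statistical sections in the protocol". Under SAP 4.7.1.2, TEA change at each visit "will be compared in each IXT-m200 group versus the placebo group using a Kruskal-Wallis test", and no covariate or stratum is named. The reason given is that "it is unlikely the values will meet the necessary normality assumptions for MMRM or ANCOVA". The reported effect is "the Hodges-Lehmann estimate and 95% confidence intervals for the difference in group medians", which follows the estimand in SAP Table 2: "The difference in group medians for the change from screening in participant-rated quality of life at Week 13, 25, and 33".

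The same SAP keeps the METH-use stratum in the primary ANCOVA (4.6.1) and in the stratified Mantel-Haenszel responder analysis (4.7.1.2). SAP 4.13 declares no departure from the protocol's analyses. SAP 1.2 records: "The study was stopped before enrolling Cohort 2".

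**The concern.** The SAP's argument concerns the shape of the TEA distribution. It justifies working on ranks, but says nothing about why the screening score and the randomization stratum should go. A rank method can hold both.

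Subtracting the screening score is not the same as adjusting for it. Let rho be the correlation between screening and follow-up TEA, and k the screening SD divided by the follow-up SD. In a linear model the slope of change on screening score is rho/k - 1. This is zero only when rho = k. Otherwise the change score still depends on where the participant started, so chance imbalance in screening TEA stays in the comparison.

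The samples are small: about 40 versus 20, and possibly fewer at later visits, since missing TEA is not imputed (SAP 4.1.2) and dropout may reach 50% (SAP 2.2). TEA is the first-listed secondary endpoint in a trial meant to inform Phase 3. Group means and SDs are still tabulated (SAP 4.1.1), so information on variability is not lost. What suffers is the precision of the between-group comparison.

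**Working it through.** **Inputs from the documents.** Cohort 1 is randomized 2:1, about 40 versus 20 (SAP 1.2). Alpha is two-sided 5%, nominal (SAP 4.1.1). TEA ranges from 4 to 40 (SAP 4.7.1.2). Dropout is up to 50% (SAP 2.2).

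**Inputs that are assumed.** The documents give no rho, SD or treatment effect for TEA. I use rho 0.3/0.5/0.7, k from 0.5 to 1.3, and effects of 0.3, 0.5 and 0.8 follow-up SD.

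**Step 1. The plan's own figure.** SAP Table 4 gives a detectable difference of 0.78 pooled SD for 40 versus 20 at 80% power. A noncentral-t calculation gives 0.780, so it reproduces. The figure concerns the primary endpoint, but it shows that 0.8 SD is about the effect this sample can detect.

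**Step 2. Variance of the adjusted comparison relative to raw change.**

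Ratio = (1 - rho²) / (1 + k² - 2·rho·k)

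Example, k = 1 and rho = 0.5: 0.75 / (2 - 1) = 0.75.

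| k | rho 0.3 | rho 0.5 | rho 0.7 |
|---|---|---|---|
| 0.5 | 0.96 | 1.00 | 0.93 |
| 0.7 | 0.85 | 0.95 | 1.00 |
| 1.0 | 0.65 | 0.75 | 0.85 |
| 1.3 | 0.48 | 0.54 | 0.59 |

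The ratio never exceeds 1 and equals 1 only when rho = k.

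**Step 3. Simulated power, 40 versus 20, 0.8 SD effect.** There were 12,000 trials per setting. Scores were rounded and clipped to 4-40, with follow-up SD 6 and a 0.3 SD difference between two equal strata. The rank ANCOVA regresses the rank of change on treatment, rank of screening TEA and stratum. Entries are for rho 0.3/0.5/0.7.

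| k | Kruskal-Wallis, % | Rank ANCOVA, % | Gain, points |
|---|---|---|---|
| 0.5 | 81.1/88.7/96.3 | 82.6/88.9/97.2 | 1.5/0.2/0.9 |
| 0.7 | 76.4/86.8/97.1 | 82.3/88.6/97.1 | 5.9/1.8/0.0 |
| 1.0 | 65.0/79.2/94.3 | 81.0/88.7/97.0 | 16.0/9.5/2.7 |
| 1.3 | 53.3/66.7/84.3 | 81.1/88.2/96.4 | 27.8/21.5/12.1 |

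- Smaller effects, k = 1: at 0.5 SD, 30.9/40.3/59.9% against 43.0/50.1/67.0%. At 0.3 SD, 14.0/17.5/26.3% against 18.5/21.7/31.1%.
- 20 versus 10 (50% dropout unrelated to screening TEA), 0.8 SD: with k = 1, 36.5/47.7/69.6% against 49.6/57.8/75.1%. With k = 0.5, 50.4/59.5/72.3% against 51.3/59.0/75.2%, so no gain at rho 0.5.
- SD of the estimate in TEA points, k = 1, 40 versus 20: Hodges-Lehmann 1.97/1.71/1.35, ANCOVA 1.59/1.42/1.19. Under the simulated shift model both estimate the same shift.
- Null rejection with complete data: Kruskal-Wallis 4.4-5.3%, rank ANCOVA 4.7-5.4%.

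**Step 4. Other score shapes.**

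- Skewed scores (gamma, shape 2), k = 1, 0.8 SD: 71.6/85.0/96.4% against 85.2/91.8/97.9%.
- A separate set of 32 settings covered normal scores, bounded integer scores, a strong ceiling and heavy tails, with rho 0.2 to 0.8, at 40 versus 20 and 20 versus 10. Kruskal-Wallis was below rank ANCOVA in all 32. It beat linear ANCOVA in two, both with heavy tails and rho 0.8. These runs scaled screening and follow-up alike, so they say little about k below 1.

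**Step 5. Dropout that depends on screening TEA (hypothetical, k = 1, no treatment effect).** Dropout was 30% or 50% at mean screening TEA, with about 4,000 trials per setting.

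- Opposite dependence by arm (log-odds slope -0.7 and +0.7 per SD): Kruskal-Wallis rejects in 6.4-14.1%, rank ANCOVA in 4.9-5.8%. Bias is 0.7-2.6 TEA points for Hodges-Lehmann and at most 0.05 for ANCOVA.
- Dependence in the active arm only: Kruskal-Wallis 5.3-7.9%.
- The same dependence in both arms: Kruskal-Wallis 4.0-5.3%.

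**The case against.** The SAP chose a valid test, gave its reason, and reports an estimate aligned with its median-difference estimand. Change from screening is also the protocol's own endpoint. The trial was not powered for any effect and its p-values are nominal, so preferring a more efficient test may look like taste. Every figure for the loss rests on an assumed rho and SD ratio, and plausible values give no gain. The bias results need dropout to depend on screening TEA differently by arm, which nothing in the documents suggests, and participants who stop dosing can stay on a schedule that includes TEA (protocol 1.3.3). Supportive analyses can be added without an amendment (SAP Introduction), and subgroup analyses by baseline METH use are allowed (SAP 4.12). Finally, the plan lets the Sponsor see group-level interim data, so replacing the main test now could follow knowledge of results.

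Much of this stands as a limit on size: the harm is modest, the dropout result should carry little weight, and the gain can be nil. It does not rescue the rationale, because non-normality gives no reason to drop either covariate. Optional subgroups and unspecified supportive analyses do not put adjustment into the planned comparison. The timing point calls for disclosure; the SAP's Introduction allows changes to planned analyses before database lock.

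**Conclusion.** The concern holds. The SAP replaces an adjusted analysis with an unadjusted one for a reason that supports only the move to ranks. With complete data, or dropout whose relation to screening TEA does not differ by arm, the test is valid and the cost is precision. At 40 versus 20 and a 0.8 SD effect, the power lost against rank ANCOVA runs from about 0 points (k of 0.5 to 0.7 with rho 0.5 or more) to 3-16 points at equal SDs and 12-28 points at k = 1.3. For a 0.3 SD effect at equal SDs it is 4 to 5 points. Confidence in the size is medium, because rho, k and the effect are all assumed. Bias is possible only under the differential dropout pattern of step 5. The change should be made, as an inexpensive improvement to a secondary analysis. The inaccurate statement in SAP 4.13 is a documentation matter and does not raise the severity.

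**What to change.** - In SAP 4.7.1.2, test TEA change at each visit by rank ANCOVA on treatment, ranked screening TEA and METH-use stratum.
- Keep the Hodges-Lehmann shift and label it as unadjusted. Beside it, report as support an ANCOVA mean difference with 95% CI, adjusted for screening TEA and stratum.
- In Table 2, state that the adjusted figure is a mean difference and not the median-difference estimand.
- In SAP 4.13, list the departure from the protocol's TEA model, and say whether group-level interim results were known when the test was changed. If the database is already locked, report the adjusted analyses as supportive in the clinical study report.

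The cost is SAP wording and a few lines of code, with no new data. There are two drawbacks. The rank test and the supportive interval target different quantities and may not agree exactly. Separate tests by visit also do not restore the protocol's repeated-measures, missing-at-random structure.

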Objective: To evaluate the efficacy of IXT-m200 in increasing the number of participants	Endpoints: Responders at Week 25 as measured by the DSM-5 criteria. A responder is a participant who meets the definition of early remission, i.e., ≥3 months and <12 months without meeting DSM-5 criteria, while disregarding the result for craving.	
achieving early remission.	Clinical Question: Does adding IXT-m200 to standardized CBT program improve the proportion of participants achieving early remission, relative to the CBT program alone in treatment-seeking participants regardless of IXT-m200 interruption or discontinuation, for any reason?	
	Estimand: The difference in the proportion of responders between the IXT-m200 and placebo groups, where a responder is a participant who meets the definition of early remission, i.e., ≥3 months and <12 months without meeting DSM-5 criteria, other than craving. All observations will be used, regardless of whether a participant discontinued treatment early. All missing values will be imputed assuming the participant has not achieved early remission.	
Objective: To evaluate the efficacy of IXT-m200 in improving	Endpoints: Difference between groups in Clinical Global Impression of Change (CGIC) at Week 13, 25, and Week 33.	

clinician-rated response to treatment.	Clinical Question: Does adding IXT-m200 to standardized CBT program improve CGIC at Week 13, 25, and Week 33, relative to the CBT program alone in treatment-seeking participants regardless of IXT-m200 interruption or discontinuation, for any reason? Estimand: The difference in CGIC at Week 13, 25, and Week 33, between the IXT-m200 and placebo groups in treatment-seeking individuals with MUD. All observations will be used, regardless of whether a participant discontinued treatment early. Missing values will not be imputed.

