Objective: To evaluate the efficacy of IXT-m200 in improving patient-rated response to treatment.	Endpoints: Difference between groups in Patient Global Impression of Change (PGIC) at Week 13, 25, and Week 33. Clinical Question: Does adding IXT-m200 to standardized CBT program improve PGIC at Week 13, 25, and Week 33, relative to the CBT program alone in treatment-seeking participants regardless of IXT-m200 interruption or discontinuation, for any reason? Estimand: The difference in CGIC at Week 13, 25, and Week 33, between the IXT-m200 and placebo groups in treatment-seeking individuals with MUD. All observations will be used, regardless of whether a participant discontinued treatment early. Missing values will not be imputed.

Table 3 Exploratory Efficacy Objectives and Endpoints

Exploratory Objectives	Endpoints
To evaluate the efficacy of IXT-m200 in increasing the number of participants achieving early remission.	Responders at Week 33 as measured by DSM-5 criteria. A responder is a participant who meets the definition of early remission, i.e., ≥3 months and <12 months without meeting DSM-5 criteria while disregarding the result for craving.
To evaluate the efficacy of IXT-m200 in reducing the number of adverse outcomes from the Adverse Outcomes Assessment.	The difference between groups in the number of adverse outcomes reported at Week 13, 25, and Week 33.
To evaluate the efficacy of IXT-m200 in preventing or reducing relapse to stimulant use, as measured by self-report surveys.	Percent of days abstinent from stimulants following a 4-week grace period (between Week 5 and Week 25) as measured by self-report.
To evaluate the efficacy of IXT-m200 in improving the length of sustained abstinence.	Number of sequential weeks of abstinence from the end of treatment visit (Week 25), defined as four weeks after the final planned dose of study drug (at Week 21), as measured by saliva screens.
To evaluate the efficacy of IXT-m200 in improving post-treatment abstinence.	Point prevalence abstinence (last 7 days) as measured by saliva screens at Week 25, Week 29, and Week 33.
To evaluate the efficacy of	Complete abstinence during the last month of study drug treatment (between Week 21 and Week 25), as measured by saliva screens.

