4.1.1. Common Statistical Methods and Data Presentations

Descriptive and inferential statistics will summarize results. Unless otherwise indicated, the prespecified efficacy analyses will be conducted using the ITT population. The study will use an overall nominal two-sided Type I error rate of 5%; results will be reported with a two-sided 95% confidence interval (CI) and nominal p-value. For primary and selected secondary and exploratory efficacy outcomes, plots of the cumulative distribution functions (CDFs) will show differences by treatment arm.

Categorical variables will be summarized with the frequency count and percentage of participants with non-missing data. Continuous variables will be summarized using appropriate summary statistics (e.g., the number of non-missing observations, mean, standard deviation (SD), median, 25th and 75th percentiles, minimum, maximum; geometric mean and 95% confidence intervals (CIs) may also be presented, as appropriate).

All summaries will be by treatment group. Tabular presentations will display a separate column for each treatment regimen and graphical summaries will color-code each treatment regimen.

In addition to tabular and graphical summaries, by-participant listings will present all relevant electronic case report form (eCRF) data, sorted by treatment group and participant identifier.

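### CGIC and PGIC have no named between-group effect measure, so only a p-value and by-arm percentages are specified; the TEA estimate needs relabelling and two Table 2 entries need repair

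*SAP*

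**What the plan says.** **CGIC.** SAP 1.1, Table 2, defines the estimand as "The difference in CGIC at Week 13, 25, and Week 33, between the IXT-m200 and placebo groups in treatment-seeking individuals with MUD". It does not say whether the difference is in means, medians, proportions or a probability. SAP 4.7.1.2 then states: "The comparison between groups will be conducted using a nonparametric Kruskal-Wallis test". Beyond that it asks for the percentage of participants in each of the seven categories, by arm and visit, and a frequency polygon at Week 25.

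**PGIC.** The analysis text has the same form. In Table 2 the objective, endpoint and clinical question concern PGIC, but the estimand line reads "Estimand: The difference in CGIC at Week 13, 25, and Week 33, between the IXT-m200 and placebo groups".

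**TEA.** The Table 2 estimand is "The difference in group medians for the change from screening in participant-rated quality of life at Week 13, 25, and 33". In SAP 4.7.1.2 the score is a sum ("minimum = 4, maximum = 40"), and the change is "compared in each IXT-m200 group versus the placebo group using a Kruskal-Wallis test". The reported estimate is "the Hodges-Lehmann estimate and 95% confidence intervals for the difference in group medians".

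**General rule.** SAP 4.1.1 says "results will be reported with a two-sided 95% confidence interval (CI) and nominal p-value".

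**Missing global impressions.** Table 2 says that missing CGIC and PGIC values are left unimputed. SAP 4.1.2 fills them with the neutral no-change category.

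**Protocol.** Protocol 9.4.9, Table 2, planned an ANCOVA with treatment and stratum for both scales. SAP section 1 says that the SAP prevails where the two differ.

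**The concern.** A Kruskal-Wallis test gives a p-value and no estimate. Without a named effect measure, the interval promised in SAP 4.1.1 has nothing to describe for CGIC and PGIC. The protocol's ANCOVA would have given a mean difference with an interval. The SAP removes that analysis without putting another estimate in its place, and SAP 4.13 reports no changes from the protocol's analyses.

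This matters because of the trial's stated purpose. SAP 2.2 says that the sample size was chosen to learn about treatment effect and variability for Phase 3. SAP 4.1 says that the plan should show how useful each endpoint is for measuring a treatment effect. With nominal p-values and about 60 participants, estimates and intervals are the main product of the secondary analyses.

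The TEA issue is narrower. Hodges-Lehmann estimates the median of all active-minus-placebo pairwise differences, and the SAP labels it as a difference between two medians.

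**Working it through.** **Step 1. Estimand against analysis, summary measure only.**

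| Secondary endpoint | Measure in SAP Table 2 | Estimate and interval in SAP 4.7.1.2 |
|---|---|---|
| TEA | Difference in group medians | Hodges-Lehmann with 95% CI |
| Early remission, Week 25 | Difference in proportions | Risk difference with score limits |
| CGIC | None named | None named |
| PGIC | None named, and written for CGIC | None named |

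Two of the four endpoints have an estimate and interval, so their absence for CGIC and PGIC looks like an omission and not a policy.

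**Step 2. The choice of measure matters on a seven-point scale.** The documents give no CGIC data, so these category probabilities are assumed (1 = very much improved, 7 = very much worse):

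- Active: 0.20, 0.25, 0.20, 0.20, 0.08, 0.05, 0.02
- Placebo: 0.10, 0.20, 0.22, 0.28, 0.10, 0.07, 0.03

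Results:

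- Mean difference: 2.94 − 3.41 = −0.47.
- Medians: 3 and 3. Cumulative probability passes 0.5 at category 3 in both arms (0.65 and 0.52).
- Top two categories: 0.45 − 0.30 = +0.15.
- P(active better) + ½ P(tie) = 0.5005 + ½ × 0.1821 = 0.592.

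One pair of distributions thus gives no difference in medians and a clear difference on the other measures. The SAP does not say which is meant.

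**Step 3. Precision that the p-value does not show.** SAP 1.2 says that the study stopped before Cohort 2, so the planned comparison is about 40 versus 20. Simulating Step 2 at those sizes gives a standard error of 0.075 for the probability. The 95% half-width is 1.96 × 0.075 = 0.147, or about 0.445 to 0.739 around 0.592. With two groups, the Kruskal-Wallis p-value equals the asymptotic Wilcoxon rank-sum p-value (0.2093 for both in a test dataset). The Mann-Whitney probability is therefore the measure that this test addresses.

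**Step 4. TEA: difference in medians against Hodges-Lehmann.** Assume that responders change by N(12, SD 6) and others by N(1, SD 4), with responder fraction p on active and q on placebo.

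- Each group median solves p·Φ((x − 12)/6) + (1 − p)·Φ((x − 1)/4) = 0.5, with q in place of p for placebo.
- The Hodges-Lehmann target is the median of the pairwise differences, a mixture of N(0, √72), N(11, √52), N(−11, √52) and N(0, √32) with weights pq, p(1 − q), (1 − p)q and (1 − p)(1 − q). The second entry is the SD.

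| p vs q | Group medians | Difference in medians | Hodges-Lehmann | Gap | SE of Hodges-Lehmann, 40 vs 20 (simulated) |
|---|---|---|---|---|---|
| 35% vs 15% | 3.43, 1.81 | 1.62 | 1.81 | 0.19 | 1.64 |
| 45% vs 20% | 4.65, 2.14 | 2.50 (rounded) | 2.50 | 0.00 | 1.76 |
| 60% vs 30% | 7.13, 2.94 | 4.19 | 3.40 | 0.79 | 2.00 |

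Rounding each score to an integer gives 1 vs 2, 3 vs 2 and 4 vs 3, but each of those gaps is a single rounding step. Under a pure shift of 4 points the two quantities agree (4.1 vs 4.0 by simulation). More extreme assumptions separate them further. Responders at N(18, SD 4) and others at N(2, SD 4), 55% vs 30%, give 8.5 vs 3.8. Equal medians with opposite skew give 0.0 vs 2.3.

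**Step 5. The missing-data conflict changes the answer.** Take Step 2 with half of each arm missing; SAP 2.2 cites dropout of up to 50%. With no imputation, and values missing completely at random, the expected results stay at −0.47 and 0.592. With the no-change rule, each probability is halved and 0.5 is added to category 4. The mean difference becomes 0.5 × (−0.47) = −0.235, and the probability of a better rating becomes 0.545.

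**The case against.** The best case for the plan has four parts.

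1. **The category table carries the information.** With the group sizes, any ordinal effect measure can be worked out from the by-arm percentages. This is right, so a reader should not infer that the report would be silent on CGIC and PGIC. But the plan specifies no between-group estimate or interval, and one computed later would be chosen after the results were seen.
2. **Hodges-Lehmann beside a two-group rank test is a common convention.** It is exact under a location shift. A reader might infer that the TEA figure would be wrong, but the documents give no TEA distribution from which to show that. In the moderate mixtures the gap lies well inside sampling error. Nor is it a fault that the TEA plot shows group medians while the table shows a between-group estimate, because they are different summaries.
3. **The PGIC line is a copy error.** The objective, endpoint, clinical question and analysis section all say PGIC. The documents do not support the inference that the patient scale would be analysed with clinician ratings.
4. **The Mann-Whitney probability is one of several valid measures.** A proportional-odds model or a top-two-category risk difference would also serve. What the plan needs is one named measure; this one simply fits the planned test.

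**Conclusion.** The main point stands: the SAP defines no effect measure for CGIC or PGIC and plans no between-group estimate or 95% interval for them, contrary to SAP 4.1.1 and to the aim in SAP 2.2. The ±0.15 half-width rests on assumed category probabilities and 40 versus 20.

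The TEA point is one of labelling. Its size depends wholly on the assumed distributions and is probably small relative to sampling error.

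It would be tempting to say that three of the four secondary estimands contradict their analyses. The text does not bear that out: CGIC is unspecified rather than mismatched, PGIC adds a copy error, and TEA matches under a shift assumption that is not stated. The early-remission endpoint is not thereby cleared. Its effect measure matches, but Table 2 counts all missing values as non-remission while SAP 4.7.1.2 leaves out some early withdrawals and participants without use data.

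The weight is moderate. These are secondary endpoints with nominal p-values in an exploratory trial, and the primary analysis is untouched.

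**What to change.** - **CGIC and PGIC, SAP Table 2 and 4.7.1.2.** Define the estimand as the probability that a participant on IXT-m200 has a better rating than one on placebo, ties counted half. Report it with a 95% interval beside the Kruskal-Wallis p-value at Weeks 13, 25 and 33.
- **PGIC row, Table 2.** Replace CGIC with PGIC in the estimand.
- **TEA, Table 2 and 4.7.1.2.** Call the estimand and the estimate the Hodges-Lehmann shift, the median of pairwise differences. Group medians need no new output, since SAP 4.1.1 and the TEA plot already provide them.
- **Missing CGIC and PGIC values.** Choose between no imputation (Table 2) and the no-change rule (4.1.2), and state the same rule in both places.
- **SAP 4.13.** Record the move from ANCOVA to a rank test for these scales.

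The cost is SAP wording and one extra output column, with no new data. SAP section 1 allows amendment before database lock; after that, the change belongs in the clinical study report. Since the sponsor may have seen group-level interim data (SAP 2.4.1), the measure should be chosen without reference to by-arm CGIC or PGIC results.
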